5.1 Inclusion Criteria

- All participants will need internet access to complete the initial surveys and the diaries.

Non-dysfunction participants

Inclusion criteria:

- Adult (over 18 years old) cis-gender female
- Neurologically stable
- Sexually active at least once per month
- Able to understand consent and communicate effectively with research team

Non-SCI dysfunction participants

Inclusion criteria:

- Adult (over 18 years old) cis-gender female
- Neurologically stable
- Sexually active at least once per month

- Sexual dysfunction, per short-form FSFI score below 19
- Lubrication difficulties, per short-form FSFI lubrication subdomain score below or equal to 3
- Able to understand consent and communicate effectively with research team

Spinal cord injured participants

Inclusion criteria:

- Adult (over 18 years old) cis-gender women
- Clinically diagnosed spinal cord injury (AIS A-B) at vertebral level within C6-T10 at least six months prior or clinically diagnosed spinal cord injury (AIS C) at vertebral level within C4-T10 at least six months prior
- Nominally sexually active, but at minimum interest in sexual pleasure even if fully self-induced
- Sexual dysfunction, per short-form FSFI score below 19
- Able to understand consent and communicate effectively with research team

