1.1 Background and Significance

Female sexual health is an important determinant in quality of life, contributing to both increased meaning in life and general well-being [1]. Unfortunately, approximately 41% of women suffer from female sexual dysfunction (FSD) [2]. There are several domains that contribute to sexual dysfunction. Difficulty with genital arousal can arise from low activity in the nerves or blood vessels of the genitals. Problems with low sexual interest can stem from hyperactivity in the brain. Some women suffer from FSD due to neurological conditions such as spinal cord injury (SCI). After injury, neural connections between central sexual function neural circuits (e.g. desire) and peripheral sexual functions (e.g. genital arousal) are interrupted. Although not a factor in mortality, sexual function remains a critical component of quality of life after SCI and is frequently reported as a high priority for restoration [3], [4].

A challenge in studying sexual function in women is the complexity of sexual arousal, which includes both cognitive desire and genital arousal components [5]. Overall female sexual function is not well understood, which contributes to the lack of good treatment options for dysfunction, regardless of type. Pharmaceuticals such as sildenafil (viagra) have occasionally been reported to improve genital arousal [6] but results are inconsistent and frequently present with mild to moderate side-effects [7]. There is a need for an effective treatment for women who have genital arousal deficiencies without concurrent side-effects. The ultimate goal of this research is to provide improvement in genital sexual arousal for women FSD due to either neurogenic (i.e. SCI) or non-neurogenic causes.

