1.2 Objective

The overall purpose of this research is to improve sexual function in women with sexual dysfunction. The goal of this study is to see if either of two nerve stimulation interventions cause a short-term change in vaginal blood flow. The effect of this intervention will be compared between women who have neurogenic (spinal cord injury) or non-neurogenic dysfunction and healthy women, to reveal mechanisms underlying neural control over vaginal blood flow.

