5.2 Exclusion Criteria

Non-dysfunction participants

Exclusion criteria:

- Male
- Pregnancy or planning to become pregnant during study period
- Sexual dysfunction, per short-form FSFI score below 19
- Lubrication difficulties, per short-form FSFI lubrication subdomain score below or equal to 4, or per investigator's discretion.
- Clinically diagnosed bladder dysfunction, pelvic pain, or other pelvic organ symptoms
- Suspected or diagnosed epilepsy
- Active infection or active pressure sores in the perineal region
- Implanted pacemaker or defibrillator
- Currently has or tested positive in the last 14 days for COVID-19 or is symptomatic for COVID-19.

Non-SCI dysfunction participants

Exclusion criteria:

- Male
- Pregnancy or planning to become pregnant during study period
- Clinically diagnosed bladder dysfunction, pelvic pain, or other pelvic organ symptoms
- Suspected or diagnosed epilepsy
- Active infection or active pressure sores in the perineal region
- Implanted pacemaker or defibrillator
- Currently has or tested positive in the last 14 days for COVID-19 or is symptomatic for COVID-19.

Spinal cord injured participants

Exclusion criteria:

- Male

- Spinal cord injury at or above C5 level (C1-C5) if AIS A or B, or spinal cord injury at or above C3 level (C1-C3) if AIS C
- Spinal cord injury below T10 vertebral level or reflexes not preserved
- Acute worsening in motor or sensory function in the last month
- Suspected or diagnosed epilepsy
- Pregnancy or planning to become pregnant during study period
- Active infection or active pressure sores in the perineal region
- Implanted pacemaker or defibrillator
- Currently has or tested positive in the last 14 days for COVID-19 or is symptomatic for COVID-19.

6. Study Sites

All research activities will be performed at University of Michigan Health System locations, also known as Michigan Medicine. The two electoral stimulation sessions will be performed at MCRU sites at Domino's Farms or the Cardiovascular Center in Ann Arbor. These sites are normal clinical sites for studies of this nature. All clinical team members have full clinical privileges at both locations and see patients at both locations. All members of the research team hold primary appoints within the University of Michigan Medical School.

7. Informed Consent

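### The dysfunction groups enter on different rules and the ANOVA does not adjust for age, so a participant-type difference cannot be attributed to spinal injury alone

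*Combined protocol and SAP*

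**What the plan says.** Section 1.2 sets a between-group purpose: the effect is compared across neurogenic, non-neurogenic and healthy women "to reveal mechanisms underlying neural control over vaginal blood flow". Sections 1.4 and 3.2 carry this out with an ANOVA on VPA whose listed factors are participant type, location and interval.

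Sections 5.1 and 5.2 define the groups. Both dysfunction groups share one line: "Sexual dysfunction, per short-form FSFI score below 19". The non-SCI dysfunction group must also meet "Lubrication difficulties, per short-form FSFI lubrication subdomain score below or equal to 3" and "Sexually active at least once per month", and is closed to women with a diagnosed bladder problem, pelvic pain or another pelvic organ complaint. The SCI group has no lubrication rule and no such pelvic exclusion, and its activity rule reads "Nominally sexually active, but at minimum interest in sexual pleasure even if fully self-induced". Its remaining rules mostly concern the injury, for example the exclusion "Spinal cord injury below T10 vertebral level or reflexes not preserved".

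The only age rule, in all three groups, is over 18. No matching or stratification by age is described. Section 3.2 does use age, BMI and FSFI score, but in a separate regression on the maximal VPA response that is not said to adjust the group comparison.

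**The concern.** The groups are not randomised, so a difference between them points to spinal pathways only if they are otherwise comparable in whatever drives the VPA response. Two features work against that.

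First, the additional lubrication rule bears on what the outcome measures. Section 1.1 says "There are several domains that contribute to sexual dysfunction" and separates genital arousal from desire. Section 2.2 names lubrication as a genital arousal response and VPA as the standard measure of genital arousal. One dysfunction group is thus chosen for self-reported poor genital response, while the other may qualify through any mix of domains. The activity and pelvic-symptom rules differ as well.

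Second, the plan itself regards age as possibly related to VPA response, yet neither the design nor the ANOVA controls it.

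At stake is the reading of the participant-type term. A larger response in SCI women than in non-SCI women with dysfunction could come from the entry rules or from an age gap.

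**Working it through.** **Plan's own figure.** Section 3.1 gives 10 healthy + 10 non-SCI dysfunction + 20 SCI = 40, which agrees with the stated target. There is no effect size, SD or power statement to reproduce.

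**Step 1: the rules side by side (sections 3.1, 4, 5.1, 5.2).**

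| Rule | Non-SCI dysfunction | SCI |
|---|---|---|
| Short-form FSFI total | below 19 | below 19 |
| Short-form FSFI lubrication | 3 or less | none |
| Sexual activity | monthly | nominal; interest suffices |
| Diagnosed pelvic organ condition | excluded | not excluded |
| Age | over 18 | over 18 |
| Main recruitment route | online portal, gynecology flyers; clinics possible | study clinicians' practice |
| Planned number | 10 | 20 |

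The healthy group has the same activity rule and pelvic exclusion as the non-SCI dysfunction group, and excludes lubrication of 4 or less.

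**Step 2: which contrasts are exposed.** Write the mean response of group g at site s as the true effect plus a shift B(g) due to selection or age.
- Genital minus tibial within one group (Aims 1 to 3): B(g) − B(g) = 0. Each woman receives both sites, so these comparisons are not affected.
- SCI minus non-SCI dysfunction at one site, or averaged over sites: B(SCI) − B(FSD) remains.
- Group-by-location, the difference between groups in genital minus tibial: the shift cancels if it is the same at both sites. It remains only if B depends on site.

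The outcome is a change from each woman's own baseline. That removes differences in level but not differences in responsiveness, which is what B represents.

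**Step 3: shift from the lubrication rule.** If a share f of SCI women score above 3 and respond by d more than women at 3 or less, the contrast shifts by f × d. For f assumed at 25% to 75% this is 0.25d to 0.75d. The documents give neither f nor d, so this shows how the bias arises but not how large it is.

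**Step 4: shift from age.** With an assumed age SD of 12 years, the standard error of a chance difference in mean age is 12 × √(1/10 + 1/20) = 4.6 years for 10 vs 20, and 12 × √(2/10) = 5.4 years for 10 vs 10. Ordinary sampling error already covers such chance gaps; only a systematic gap biases the contrast. For a systematic gap, bias in SD of response = correlation × gap in SD of age. The false-positive rates below come from simulation (20,000 runs per case, 10 vs 20, no true group effect, linear age effect, two-sided 5% test).

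| Assumed age gap | Assumed correlation | Bias (SD) | False positives, no age term | With age term |
|---|---|---|---|---|
| 0.5 SD | 0.3 | 0.15 | 6.7% | 5.0% |
| 0.5 SD | 0.5 | 0.25 | 9.5% | 4.9% |
| 1.0 SD | 0.3 | 0.30 | 11.7% | 4.8% |
| 1.0 SD | 0.5 | 0.50 | 23.9% | 4.9% |

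**Step 5: precision of a restricted contrast.** The difference detectable with 80% power at two-sided 0.05 is (1.960 + 0.842) × √(1/10 + 1/n), by normal approximation. For n = 20 SCI women it is 1.09 SD. If 15, 10 or 5 of the 20 have lubrication of 3 or less (assumed), it is 1.14, 1.25 or 1.53 SD.

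**The case against.** The strongest reply is that the plan's mechanistic argument does not rest on the exposed contrast. The three aims are within-woman comparisons. The end of section 1.1 says the information on neural circuitry will come from whether either stimulation approach works better in spinally intact or damaged participants, which can be read as a group-by-location question. This stands, with one limit: neither 1.4 nor 3.2 names that interaction, while both list participant type as a factor. A reader might infer that the group comparison can say nothing about spinal pathways. The documents do not support that.

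A reader might also infer that the SCI group will be largely women with normal lubrication. Nothing in the documents shows this. Section 1.1 says the injury interrupts connections to genital arousal, and section 5.2 counts scores up to 4 as a lubrication difficulty in controls, so above 3 does not mean normal.

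Nor do the recruitment routes establish an age gap between controls and non-SCI women with dysfunction: section 4 gives both the same main route. An SCI versus non-SCI gap is possible because the routes differ, but it is not certain.

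Finally, restricting SCI women by lubrication conditions on something the injury may itself change. It leaves the pelvic-symptom exclusion unequal and leaves few women. That argues against letting such a subset decide the interpretation, but not against reporting it. The pilot status limits how much remedy is reasonable; it does not remove the need to say what a group difference can mean.

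**Conclusion.** The concern holds for the participant-type main effect and for group differences at a single site. The differences in lubrication, activity and pelvic-symptom rules are built into the design. An age difference is an uncontrolled risk, not an established fact. Either could produce a group difference without any effect of the spinal injury.

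It does not extend to Aims 1 to 3, and it reaches a group-by-location contrast only if the shift differs between sites.

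The size of the bias cannot be derived from the documents. The range of 0.15 to 0.50 SD, with false-positive rates of about 7% to 24%, depends wholly on the assumed systematic age gap and the assumed linear age-response correlation. No figure can be given for the lubrication rule.

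**What to change.** In section 3.2:

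1. Include age as a covariate in the participant-type comparison. Age is already planned for the regression there. The cost is one degree of freedom: for three groups in 40 women, between-women residual degrees of freedom go from 40 − 3 = 37 to 36.
2. State that group main effects are exploratory and not attributable to spinal injury alone, because the entry rules differ on lubrication, activity and pelvic symptoms. This costs only wording.
3. As a descriptive sensitivity analysis, also report the SCI versus non-SCI dysfunction contrast in SCI women with lubrication of 3 or less. Use the short-form FSFI already required at screening, so that the cut-off is on the same scale in both groups. The cost is one extra table, with low precision.

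The subset should not override the full-group result. No change to SCI eligibility and no recruitment of controls to age bands is needed.

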5.2 Exclusion Criteria

Non-dysfunction participants

Exclusion criteria:

- Male
- Pregnancy or planning to become pregnant during study period
- Sexual dysfunction, per short-form FSFI score below 19
- Lubrication difficulties, per short-form FSFI lubrication subdomain score below or equal to 4, or per investigator's discretion.
- Clinically diagnosed bladder dysfunction, pelvic pain, or other pelvic organ symptoms
- Suspected or diagnosed epilepsy
- Active infection or active pressure sores in the perineal region
- Implanted pacemaker or defibrillator
- Currently has or tested positive in the last 14 days for COVID-19 or is symptomatic for COVID-19.

Non-SCI dysfunction participants

Exclusion criteria:

- Male
- Pregnancy or planning to become pregnant during study period
- Clinically diagnosed bladder dysfunction, pelvic pain, or other pelvic organ symptoms
- Suspected or diagnosed epilepsy
- Active infection or active pressure sores in the perineal region
- Implanted pacemaker or defibrillator
- Currently has or tested positive in the last 14 days for COVID-19 or is symptomatic for COVID-19.

Spinal cord injured participants

Exclusion criteria:

- Male

- Spinal cord injury at or above C5 level (C1-C5) if AIS A or B, or spinal cord injury at or above C3 level (C1-C3) if AIS C
- Spinal cord injury below T10 vertebral level or reflexes not preserved
- Acute worsening in motor or sensory function in the last month
- Suspected or diagnosed epilepsy
- Pregnancy or planning to become pregnant during study period
- Active infection or active pressure sores in the perineal region
- Implanted pacemaker or defibrillator
- Currently has or tested positive in the last 14 days for COVID-19 or is symptomatic for COVID-19.

6. Study Sites

All research activities will be performed at University of Michigan Health System locations, also known as Michigan Medicine. The two electoral stimulation sessions will be performed at MCRU sites at Domino's Farms or the Cardiovascular Center in Ann Arbor. These sites are normal clinical sites for studies of this nature. All clinical team members have full clinical privileges at both locations and see patients at both locations. All members of the research team hold primary appoints within the University of Michigan Medical School.

7. Informed Consent

We will explain the study verbally and in writing, and we will provide the informed consent form to the participant for review before signing. We will inform participants that the purpose of the study is to learn if electrical stimulation of certain peripheral nerves can affect vaginal blood flow. We will also explain to each participant that there will be no expected benefit to them by participating in this research study. However, it is possible (although not anticipated) that during the stimulation session participants may experience short-term improvement in sexual function. Additionally, we will also explain that the knowledge gained from this research may be beneficial for others, society, and/or science.

The research team will adopt an optional electronic informed consent procedure using SignNow. This option will be our preferred method for obtaining consent. Once an interested participant is identified, the study coordinator who will reach out to the participant over the telephone to discuss the study and either obtain consent or schedule a time call the participant after they have had a time to review the consent form. In the instance a potential participant does not have access to the internet or is not inclined to use the internet, research staff will revert back to using the standard procedure for obtaining consent on paper during the first study visit. We will recruit all potential and eligible subjects who can speak, read, and understand English.

8. Waiver of Informed Consent

We are seeking a waiver of informed consent as there are a set of surveys that get completed at the very beginning of the study and daily diaries for the two days prior to the first study visit. Subjects will be able to complete their surveys and diaries at home and at their leisure. We prefer that they are completed before the test session in order to ensure that their answers won't be affected by the treatment and so that the time spent by the participant at that session is not too long. In order to do this expeditiously, it would be simplest to send them the surveys and diaries if they agree to take part during their initial recruitment call. This means, though, that a participant could be completing surveys and diaries before formally signing the consent form if

they are not being recruited during a visit at a clinic with a study team member or if they are not doing electronic consent.

9. Confidentiality of Data

Proper, standard procedures will be followed to protect participant identities. Each subject will be assigned an identification number. Only this number will be used to identify subjects in any individual tabulation. The surveys that the patients are required to fill out as part of the study will also only use this identification number as the piece of identifying information. These surveys will only be administered and collected by the study coordinator or other research team staff. The study coordinator will have access to the patient information and code key. The study coordinator's office will have a locked door. Paper research records will be stored in a locked cabinet in the study coordinator's office. No patient-identifying information will be shared outside the research team.

Only group data is expected to be published. If individual subject data is published, then no identifying information will be included. Study files will also be maintained in a secured location. Access to computerized data will be restricted to IRB approved study personnel and password authorization will be enforced. Data collection will be limited to the study investigators and research staff. All study personnel who have access to the data will be educated regarding the need to protect confidentiality and the procedure to be followed to ensure such protection. All staff will also be required to sign a standard medical record confidentiality agreement.

10. Data Safety and Monitoring

10.1 Data Safety and Monitoring Board

All research personnel involved in this study will have completed training in the protection of human research participants. A full Data and Safety Monitoring Board will not be used for this study as it is a small study. Once data collection has begun, Drs. [name] and [name] will discuss project progression, participant safety, and overall data on a monthly basis via phone, email correspondence, or an in-person meeting. Adverse Events (AEs) will be reported promptly to the IRB and to the Medical Monitor. If multiple patients experience adverse events related to research procedures, then the Medical Monitor will be consulted to discuss whether the study should be stopped or reassessed. If there is any evidence of a pattern of unanticipated AEs (regardless of causality), or Serious Adverse Events (SAEs), then the Medical Monitor will immediately review the data.

10.2 Severity

The investigator will grade any Adverse Event signs and symptoms as mild, moderate, severe, or life threatening according to the following definitions in Table 1.

Table 1. Adverse events severity scale.

Grade	Definition
Mild:	Causing no limitation of usual activity
Moderate:	Causing some limitations of usual activities
Severe:	Causing inability to carry out usual activities
Life Threatening:	Patient was at immediate risk of death from the event

10.3 Serious Adverse Event

Serious Adverse Events (SAEs) will be identified as any adverse event (AE) that:

- Is fatal;

- Is life threatening, meaning the patient was, in the view of the investigator, at immediate risk of death from the reaction as it occurred, i.e., it does not include a reaction that, had it occurred in a more serious form or progressed, might have caused death;
- Causes a persistent or significant disability or incapacity;
- Requires or prolongs inpatient hospitalization. Inpatient hospitalization will be considered a hospitalization if is longer than 24 hours or requires an intervention to treat emergent symptomatology (non-diagnostic);
- Is a congenital anomaly or birth defect;

Other important medical events may be considered SAEs when, based upon appropriate medical judgment, they may jeopardize the patient and may require medical or surgical intervention to prevent one of the outcomes as listed in this definition. We will report all SAEs to the IRBMED, including death, due to any cause which occurs during this study and until 30 days after the last participation in the study, whether or not expected and regardless of causality.

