2.1 Pre-study surveys

Prior to the first visit, participants will complete five clinically validated surveys:

- 1 The American Urological Association Symptom Index (AUASI) bladder symptom index [19]
- 2 The Female Sexual Function Index (FSFI) [20]
- 3 Fecal Incontinence Severity Index (FISI) [21]
- 4 Patient Assessment of Constipation-Symptoms (PAC-SYM) [22]
- 5 The short-form (SF-36) quality of life survey [23], [24]

Surveys will be completed over the phone or online in REDCap, a standard clinical tool for survey data collection [25]. Each survey is included in section 29.1.

2.2 Study visits 1 & 2

The same steps will be followed for all three Aims. Participants will have two study visits. The interval between visits will be at least one month but not more than five months.

On each study day, subjects will complete a urine pregnancy test. Next, subjects will recline in a comfortable position on an elevated table, with pillows and blankets provided if desired. An MCRU staff member will be available to provide assistance, if needed, in addition to one or more clinical research team members. A vaginal plethysmography transducer (Biopac TSD204) will be inserted about 3 inches into the patient's vagina by a clinical staff member or by the patient with clinician supervision. The transducer measures vaginal pulse amplitude (VPA), the standard clinical technique for assessing genital sexual arousal in women [5], [26]–[28]. No energy is transmitted from the TSD204 to the participant. A heart rate monitor (e.g. electrocardiogram or pulse oximetry) and blood pressure monitor will be placed on the participant's arm, hand, or chest (as is appropriate per monitor) to monitor off-target autonomic responses.

On the first study day, one of the two stimulation approaches will be randomly selected and prepared. For dorsal genital nerve stimulation, two circular 1.25-inch diameter transcutaneous electrical stimulation (TENS)

[figure not shown]

Figure 1. Electrode locations (red dots) for genital nerve stimulation, on either side of the clitoris.

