2.3 Pelvic function daily diaries

To look for off-target or carry-over stimulation effects, participants will be asked to complete a daily bladder, bowel, and sexual function diary from two days before until two days after a session, to provide objective measures across several parameters (e.g. incontinence episodes, regularity). The full diary is in section 44.1. Figure 3 shows the daily questions. Surveys will be completed in REDCap or over the phone. Spinal cord injured patients will also have a question asking if they had an autonomic dysreflexia event.

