2.4 Patient timeline

Research Activity timetable summary:

1. Consent
2. Pre-session surveys

3. Study visit 1:

- Days 1 & 2: At-home diary
- Day 3: Test session and diary
- Days 4 & 5: At-home diary

4. Interval of one to five months

[figure not shown]
5. Study visit 2:

- Days 1 & 2: At-home diary.
- Day 3: Test session and diary
- Days 4 & 5: At-home diary

Bladder Function	
Did you have any leakage or incontinence?	
• None• Some• A lot
Did you need to use the bathroom at night?	
• No• Once• Multiple times
How did your bladder function compare to the prior day?	
• Worse• The same• Better
Bowel Function	
Did you have a regular bowel event?	
• No• Almost, or with help• Yes
Did you have fecal incontinence?	
• No• Once• Multiple times
How did your bowel function compare to the prior day?	
• Worse• The same• Better
Sexual Function	
Were you sexually active with a partner or by yourself?	
• No• Self• Partner
If active, did you feel genital arousal or lubrication?	
• No• Some• Yes
If active, did you have an orgasm?	
• No• Yes
Changes in Pelvic Sensation	
Did you experience any atypical sensations from your pelvic region?	
• No• Yes
If yes, please elaborate:	

Figure 3. Pelvic function daily diary questions

Figure 4 provides a visual summary of the timeline for each study participant.

3. Study Statistics and Data Analysis Plan

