3.1 Sample size

The target population size (N=40) is based on intended recruitment of 40 women; 10 normal women (e.g. without SCI nor FSD), 10 non-SCI women with FSD, and 20 women with SCI. Efforts will be made to recruit equal numbers between AIS A SCI and AIS B-C SCI participants, but it may be challenging to get exactly 10 in each SCI group. The AIS A SCI and AIS B-C SCI is based on the International Standards for Neurological Classification of Spinal Cord Injury. AIS A SCI refers to complete, no sensory or motor function SCI, while AIS B-C SCI refers to incomplete SCI (e.g. sensory but not motor function is preserved). This is a pilot study with no comparable studies for identifying an effect size and performing a power analysis. If we determine that a larger population size is needed for any participant groups, based on preliminary data analyses, then the target group size will be increased.

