11.2 Risks to Human subjects

Potential risks include release of identifying information, physical discomfort or pain during stimulation, skin irritation from gel and alcohol pad prior to electrode placement, women with SCI could have an increase in blood pressure (autonomic dysreflexia), infection from intravaginal sensors, and women with a history of trauma may feel triggered by the research intervention.

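### SAEs are to be reported for 30 days after last participation, but scheduled contact ends two days after the visit 2 session, and no diary question shown specifically asks about infection, skin injury or distress

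*Combined protocol and SAP*

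**What the plan says.** Section 10.3 requires every SAE to be reported to the IRB, whatever its cause, if it is one "which occurs during this study and until 30 days after the last participation in the study". It does not define last participation as the session or the final diary.

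Section 2.3 has participants keep a diary "from two days before until two days after a session". The timetable in section 2.4 agrees. Each visit block has "Day 3: Test session and diary", then "Days 4 & 5: At-home diary", and nothing is listed after the visit 2 block. Section 2.2 adds, on spacing: "The interval between visits will be at least one month but not more than five months".

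Figure 3 covers bladder, bowel and sexual function, followed by one open item with free text: "Did you experience any atypical sensations from your pelvic region". Women with SCI also get a question on AD (sections 2.3 and 11.2.7).

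Among the risks, section 11.2 names skin irritation from skin preparation, "infection from intravaginal sensors, and women with a history of trauma may feel triggered by the research intervention". Sections 11.2.4 to 11.2.6 say what is done if these occur.

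Section 10.1 has adverse events reported promptly. The Medical Monitor is consulted when several patients have related events, and reviews the data at once on a pattern of unanticipated events or on SAEs.

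**The concern.** The plan says how adverse events are reported, graded and reviewed, but not when or how participants are asked about them. The reporting window is much longer than the period of scheduled contact, and the questions asked within that period are not built around the risks the protocol lists.

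Three things are at stake. First, the 30-day commitment has no procedure behind it once the diary ends. Second, the section 10.1 triggers depend on several events, or a pattern of them, becoming known. The vaginal sensors are reused after sterilization (section 11.2.5), so an infection that goes unreported after one session could matter to later participants. Third, section 11.2.4 drops the skin preparation at visit 2 if it caused irritation. Irritation that appears after the woman has gone home would inform that decision only if someone learned of it.

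**Working it through.** **Timing after visit 2.**
- Inputs: session on day 3 and last diary on day 5 of each block (section 2.4); SAE window of 30 days (section 10.3).
- Last scheduled contact: 5 − 3 = 2 days after the session. This reproduces the two days stated in section 2.3.
- Clock started at the visit 2 session: 30 − 2 = 28 days without scheduled contact, and 28/30 = 93%.
- Clock started at the last diary: 30 of 30 days.

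**Timing between visits.** The months are converted to days by assumption (one month = 30 days, five months = 150 days), counted session to session. The visit 1 diary ends 2 days after the first session and the visit 2 diary starts 2 days before the second.
- Shortest gap between diaries: 30 − 2 − 2 = 26 days.
- Longest gap: 150 − 2 − 2 = 146 days.

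This gap does end in a diary and an in-person visit. Nothing comparable follows visit 2.

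**What is asked, set against the listed risks.**
- *Infection from the sensor:* no specific item. The pelvic-sensation item could prompt a report of symptoms through day 2.
- *Skin injury:* no specific item. The pelvic item could reach the genital electrode site but not the ankle, where the tibial electrodes sit (section 2.2).
- *Distress or trauma response:* no item.
- *AD:* asked directly, in women with SCI only.

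The pelvic item also depends on sensation. Section 3.1 states that "AIS A SCI refers to complete, no sensory or motor function SCI" and aims for about 10 such women among 40, so the item is unreliable in roughly a quarter of the sample.

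**What is asked at the visits.** The end-of-session questions in section 2.2 concern opinions, arousal responses and willingness to use the stimulation again. Visit 2 repeats the same steps at the other location. The only check stated for every woman on each study day before the session is the pregnancy test. No question about events since visit 1 is described.

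**Withdrawals.** Section 10.4.1 asks nothing further of a woman who withdraws, while section 10.3 makes no exception for her.

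**The case against.** A reader might infer that nothing asks about these harms and that they can be found only if a woman volunteers them. The documents do not support that. The pelvic-sensation item is asked daily in both diary blocks and has free text. Clinical staff attend both sessions and could see a skin reaction or distress. Visit 2 gives harms from visit 1 a chance to surface. Active perineal infection is an exclusion (section 5.2) and becoming ineligible is a ground for release (section 10.4.2), so staff have a reason to notice it, although no re-screen is written down.

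A reader might also add stimulation pain to the list. It does not belong there: the amplitude is set against expressed discomfort, and the current is reduced when discomfort is reported (sections 2.2 and 11.2.3).

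Nor should the diary's uneven coverage of the two electrode sites be read as biasing a planned result. Sections 1.4 and 1.5 contain no safety outcome, and no comparison of harms between genital and tibial stimulation is planned.

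Three further objections stand in part:
- Section 10.3 sets a reporting duty, not a schedule of questions, so the plan does not contradict itself. Most of the harms listed would be ordinary adverse events, not SAEs.
- The full diary is said to be in section 44.1, which is not in the documents. Figure 3 is stated to show the daily questions, so missing items are likely but not proven. The AD question shows that the figure is not exhaustive.
- Better follow-up would not confirm the stated likelihoods. With all 40 women followed and no events, the one-sided 95% upper bound is 1 − 0.05^(1/40) = 7.2%, which would not establish that an event is rare.

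These points limit the claim. None of them supplies a contact after day 2 following visit 2, or an adverse event question at visit 2.

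**Conclusion.** The concern holds in a limited form. Scheduled contact stops two days after the visit 2 session, leaving 28 of the 30 reporting days uncovered (30 of 30 if the clock starts at the last diary). No adverse event enquiry is described on arrival at visit 2, and the diary questions shown do not specifically cover infection, skin injury or distress. Later harms would therefore be found mainly if volunteered.

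The 93% is a share of days, not of events missed. The documents give no timing of onset, so the number of harms that would go unrecorded cannot be estimated. The conclusion rests on Figure 3 and the AD question being the whole diary, and on no follow-up being described in the removed pages.

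The VPA analyses are untouched. This is a cheap improvement to safety capture that should be made; it does not threaten the study's validity.

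**What to change.** 1. Send one short REDCap or phone questionnaire 30 days after visit 2, and ask the same questions on arrival at visit 2: new illness, care sought or hospital stay, infection, skin change at either electrode site, AD for women with SCI, and distress.
2. Add to the existing day 4 and 5 diary: visible skin change at the electrode site used, signs of infection that do not depend on sensation, and distress after the session.
3. In section 10.3, define last participation, and say how the 30-day duty applies to women who withdraw under section 10.4.1.

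If the section 44.1 diary already contains some of the items in step 2, only the missing ones are needed.

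The cost is a protocol amendment, a few REDCap items, one extra brief questionnaire per woman, and some coordinator time to chase non-responders. No new procedure is needed and no treatment rule changes.
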